11.0 Risks to Participants

- 11.1 Foreseeable Risks: Risks of being in the study are described in the Data and Safety Monitoring Plan of the previously approved protocol template (page 8 - 9). Below is the language copied from the protocol template with

PROTOCOL TITLE: Menthol Flavored E-Cigarette Use During a Simulated Ban of Menthol Cigarettes

VERSION DATE: 10/14/2019

additional information added to the third and fourth paragraphs regarding recent reports of respiratory illness.

Risks that subjects are exposed to as a result of enrolling in the study are minimal. Although smoking is clearly detrimental to health, we do not anticipate that their risk will increase as a result of being enrolled in the study since we will only be enrolling those who already smoke at least 5 cigarettes per day. Furthermore, any short term changes in smoking that occur as a result of either being asked to abstain from smoking menthol cigarettes or from using e-cigarettes for an 8 week period are not likely to have long term health effects.

The e-cigarettes used for this study are commercially available and among the most commonly used brands. Although these products do not currently undergo regulatory evaluation, they are easily available and increasingly being used. The risks of using e-cigarettes are not thought to be greater than of smoking (with many advocating that these products are less harmful than smoking). E-cigarettes do contain nicotine and it is possible that overuse can lead to symptoms of nicotine toxicity such as nausea, vomiting, dizziness, weakness and rapid heartbeat. The e-cigarette liquid contains propylene glycol which may be associated with throat irritation. The e-cigarette is a battery powered electronic device so malfunctions are possible.

There have been recent reports of seizures and breathing problems occurring in people who use e-cigarettes. These cases are being investigated and at this time it is not known how common these problems are or what is causing them. Since many of the cases of breathing problems occurred in individuals using e-cigarettes products with liquids that contain cannabinoid products such as THC, it is likely that the risk is due to people adding substances to e-liquids that were not intended by the manufacturer. The e-cigarette products available in the study are widely available and widely used. The devices and liquids provided to participants are not modified in any way after purchase.

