To the baseline visit, subjects will bring a first morning urine sample from which baseline urinary cotinine and total NNAL concentrations will be measured. Exhaled CO will be measured from a breath sample. Tobacco use behavior subsequent to the screening visit will be determined as will subjects' level of craving, withdrawal, motivation, self-efficacy to quit smoking, and support for a ban on a variety of menthol containing tobacco products. Subjects will then be told if they have been assigned to the condition in which they are to abstain from menthol cigarettes for the next eight weeks and will be provided (at no cost to them) with a two weeks supply of the product that they have been randomized to receive (i.e., menthol or tobacco flavored e-cigarettes, based on randomization) for the first four week period. Subjects will be instructed in how to properly use the product and will be given all of the packaging that normally accompanies the product. They will be told to use as much or as little of the product as they like. Subjects will also be provided with a tobacco use diary that they are to complete daily in which they are to record the number of cigarettes smoked and how often and how many puffs they used of their provided e-cigarette. Puffs per day has been used in other studies to evaluate e-cigarette use.^{22, 30, 31} They will additionally be asked to record use of any other tobacco or nicotine containing products. Subjects will also be asked to bring to all subsequent visits all e-cigarette cartridges as well as samples of the cigarettes or other tobacco or nicotine products that

they have been using in order to verify the accuracy of the smoking diary. Partially used cartridges will be weighed to determine the extent to which they were used. They will be given no specific instructions regarding using medicinal nicotine (i.e., nicotine patch, gum) or other tobacco products but will be asked to record any instances of using such products.

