Evaluation visits will occur at approximately 2 week intervals for eight weeks following the baseline visit. Scheduling considerations will determine the exact intervals of the visits with visits scheduled as close as possible to dates corresponding to those that would occur 2 and 4 weeks after the baseline visit and then 2 and 4 weeks after the week 4 visit (i.e., 2 and 4 weeks after they receive the alternate e-cigarette product). At the week 2 and week 6 visits, subjects will be told that they have 24 points that are worth \$1.00 per point, which they can exchange for cash or additional e-cigarette cartridges of their assigned flavor (at a cost of 3 points per cartridge, which is approximately 66% of the cost of the cartridges commercially). This approach is being used in order to better characterize how menthol vs. tobacco flavored e-cigarettes are likely to be used after subjects have become familiar with the product over the first two weeks. Providing free product for the entire four week period may result in participants using more of the product than they would otherwise use and smoke fewer cigarettes since the e-cigarettes are free and the cigarettes are not. Differences between menthol and non-menthol e-cigarette conditions may therefore be underestimated in this circumstance. Products are offered at a discount to the price available in the retail marketplace in order to ensure that any cartridges are obtained from us (rather than commercially) but to minimize hoarding of the points.

At each visit, exhaled carbon monoxide concentrations will be measured and subjects will complete questionnaires assessing craving and withdrawal symptoms, motivation to quit smoking, product liking, perceived health risks of using the product, and level of support for a ban on a variety of menthol containing tobacco products. The tobacco use diaries that subjects had been asked to complete will be collected at each visit.

At the week 4 and week 8 visits, subjects will be asked to bring a urine sample with their first morning void which will be used to measure urinary cotinine and urinary total NNAL concentrations.

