Follow up visit: Subjects will attend one follow-up visit that will occur at week 12 of the study period (i.e., four weeks after they are no longer provided e-cigarettes). To this visit, subjects will again be asked to bring their first morning urine void and an exhaled CO will be measured. The final set of tobacco use diaries will be collected. Questionnaires assessing level of craving, withdrawal, motivation and self-efficacy to quit smoking, perceived health risk, and support for a ban on a variety of menthol tobacco products will be completed as in the evaluation visits. All subjects will be provided information regarding the smoking quitline as a resource available if they are interested in quitting smoking.

As the purpose of this formative proposed project is to provide pilot data for a subsequent grant submission, subjects will be asked at the end of the study ways in which to improve future studies addressing menthol e-cigarettes (for example, asking what they would change about the study and how honest they think others were in their reporting of menthol cigarette use). Subject responses will be examined for consistent themes so as to help inform study design for future projects.

Subjects will be paid \$20 for the screening visit, the baseline visit and each of the 5 subsequent visits (i.e., visits at week 2, 4, 6, 8, and 12). Subjects who complete all scheduled visits and have complied with study related procedures will receive a \$60 bonus. Subject can therefore receive up to \$200 for completing the study in addition to payment for points that were not redeemed for e-cigarette cartridges during the final two weeks of each evaluation period. Subjects will additionally be provided bus tokens (for those who take public transportation) or parking (for those who drive) for each visit.

Data and Safety Monitoring Plan:

In this study, one-half of smokers will be asked to stop using menthol cigarettes and all smokers will be provided e-cigarettes to use over a 2 month period. Those randomized to abstain from smoking menthol cigarettes will be given no specific instructions regarding modifying their smoking

behavior in order to more closely mimic what would occur if menthol cigarettes were banned. Based on our previous research, it is expected that most will smoke non-menthol cigarettes instead.

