To ensure confidentiality, all subjects enrolled in the study will be assigned a study identification code which will be used on all study related data collection forms except for those on which the use of personal identifiers is mandatory (e.g., informed consent form). Forms that link the name of the participant and the subject identification code will be kept in a locked cabinet or office or in an electronic file stored on password protected secure computer servers that meet university guidelines. Access to subject identifiable information will be limited to those that require this information such as investigators or others who have direct contact with study subjects (e.g., study coordinator).

At each visit, subjects will be asked if they are experiencing any adverse effects or difficulties with the study. The Principal Investigator will review reports with study staff to determine if changes are needed to any of the study related procedures or if the subject has symptoms/difficulties that would warrant discontinuation from the study.

Data Analysis

The primary aim of the proposed study is to compare changes in each outcome measure (e.g., number of cigarettes smoked, amount of e-cigarette used, motivation to quit smoking, biomarker concentrations, support for a menthol ban) between the four week period when subjects are provided menthol e-cigarettes compared with the four week period when subjects are provided tobacco flavored e-cigarettes. An additional aim is to determine if cigarette type (i.e., randomization to menthol vs non-menthol) moderates the effects of e-cigarette type.

Outcomes will be described using means and standard deviations, separately for each combination of visit and experimental condition (menthol cigarettes available or not, menthol or non-menthol tobacco flavored e-cigarette). Skewed variables will be log transformed and their geometric means and 95% confidence intervals will be reported. Hypothesis testing will be performed using linear mixed models, with fixed effects for randomization group and time, and a random subject effect. The study is designed to provide pilot data to estimate broad trends and parameters that can be used

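### Perceived health risk of the e-cigarette has no scheduled value before product is issued, so change from a pre-use level cannot be reported and the ban versus no-ban comparison of this measure cannot be baseline-adjusted

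*Combined protocol and SAP*

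**What the plan says.** All of this is in the combined protocol and SAP.

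- **Screening Visit (Implementation Plan).** The only questionnaires named concern smoking history. Medical and psychiatric history is taken by self-report.
- **Baseline and Evaluation Visits, baseline part.** The questionnaire constructs are "level of craving, withdrawal, motivation, self-efficacy to quit smoking, and support for a ban on a variety of menthol containing tobacco products". Assignment is then disclosed, and product, instructions and packaging follow.
- **Baseline and Evaluation Visits, evaluation part.** The text opens with "Evaluation visits will occur at approximately 2 week intervals for eight weeks following the baseline visit". Its questionnaire list adds two items that baseline lacks, product liking and perceived risk: "motivation to quit smoking, product liking, perceived health risks of using the product, and level of support for a ban".
- **Follow up visit (week 12).** The list includes "motivation and self-efficacy to quit smoking, perceived health risk, and support for a ban on a variety of menthol tobacco products". Product liking is no longer named.
- **Data Analysis.** The primary aim is to "compare changes in each outcome measure" between the menthol and tobacco-flavor e-cigarette periods. Whether cigarette condition moderates the flavor effect is an additional aim. The mixed model has group and time as fixed effects and a random subject effect; no baseline covariate is stated. The same section counts on at least 16 subjects per group for comparing the two cigarette conditions.

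**The concern.** Craving, withdrawal, motivation and ban support are each measured before product, on product and at week 12. Perceived health risk is measured only on product and at week 12, although, unlike product liking, it does not require the subject to have used the product. The plan's own week 12 list shows this, since it asks about risk four weeks after supply ends and drops liking.

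Two things are lost. First, the study cannot say whether using the e-cigarette raised or lowered a subject's view of its risk, or whether that view had returned to its starting level by week 12. Second, between-subject differences in prior opinion stay in the error term when the ban and no-ban arms are compared. In a pilot meant to supply planning parameters, the baseline-to-follow-up correlation for this measure is also never estimated.

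**Working it through.** **1. Coverage by visit**, read from the lists above.

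| Measure | Screening | Baseline | Weeks 2, 4, 6, 8 | Week 12 |
|---|---|---|---|---|
| Craving, withdrawal, motivation, ban support | not named | yes | yes | yes |
| Perceived health risk | not named | **no** | yes | yes |

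Perceived risk is thus scheduled at 5 of the 6 visits from baseline on, and at none before product is issued.

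**2. Which contrasts need a baseline?** Let B be a subject's single pre-product value, and let M and T be the values in the menthol and tobacco-flavor periods.

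- Flavor contrast: (M − B) − (T − B) = M − T. B cancels.
- Moderation by arm: mean of (M − T) in the ban arm minus mean of (M − T) in the no-ban arm. B is again absent.
- On-product visits to week 12: both values are scheduled.
- Ban versus no-ban level: estimable without bias because the arms are randomized. B would only reduce variance.
- Change from pre-use level, M − B or T − B: not computable.

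**3. The plan's own power figure.** Inputs from Data Analysis: 40 enrolled, 15–20% attrition, standardized effect 1.0, two-sided 0.05, power about 80%.

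- Per group: 40 × 0.80 / 2 = 16, or 40 × 0.85 / 2 = 17.
- SE of an arm difference in SD units: √(2/16) = 0.354.
- Power (normal approximation): Φ(1.0/0.354 − 1.960) = 0.807. The two-sample t version gives 0.781. The stated figure is reproduced.

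**4. Precision forgone in the arm comparison.** With a baseline covariate correlated r with the outcome, SE = √((2/16)(1 − r²)). The detectable effect at 80% power is (1.960 + 0.842) × SE. The documents give no r, so the values below are assumptions.

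| r (assumed) | 1 − r² | SE (SD) | Less variance | Detectable effect (SD) |
|---|---|---|---|---|
| no baseline | 1 | 0.354 | – | 0.99 |
| 0.3 | 0.91 | 0.337 | 9% | 0.94 |
| 0.5 | 0.75 | 0.306 | 25% | 0.86 |
| 0.7 | 0.51 | 0.252 | 49% | 0.71 |

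The formula treats the outcome as one value per subject and ignores the small price of estimating the covariate slope, so the gain at r = 0.3 is slightly flattered.

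**The case against.** The case for leaving the plan alone has several parts.

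*No planned analysis depends on it.* Perceived risk is in neither aim's hypotheses, not in the Design Overview's list of assessments, and not among the example outcomes in Data Analysis. This stands and keeps the point minor. The outcome list in Data Analysis is given only as examples, however, so the measure is not excluded from the comparison of changes.

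*The visit lists are loosely drafted.* The each-visit sentence falls under a joint heading for baseline and evaluation visits. The week 12 text also says its questionnaires, self-efficacy among them, are completed as in the evaluation visits, although the evaluation list omits self-efficacy. A narrative list is weaker evidence than a schedule table. Even so, the each-visit sentence sits in text about visits after baseline, baseline has its own list, and the sentence includes product liking, which presupposes use. Omission at baseline is the better reading.

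*The existing item may not transfer.* It asks about the risk of using the product, and before assignment there is none. This stands and shapes the fix.

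*The precision gain is hypothetical.* It rests on assumed correlations and needs a covariate that the stated model lacks. This also stands.

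Two stronger readings are tempting. One is that no change at all can be computed for this measure, or that the arm comparison and week 12 have no reference. Step 2 of the working shows otherwise: the other randomized arm and the on-product visits are the references. The second starts from section 11.1, which repeats the risk text with "additional information added to the third and fourth paragraphs regarding recent reports of respiratory illness". A reader might infer that subjects entered with different warnings and so different starting perceptions. The documents do not show this. They describe an update to the risk section, not which subjects were given which wording or whether anyone was re-consented. Consent also comes at screening, before randomization, so such differences would not in themselves bias the randomized contrasts.

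**Conclusion.** The gap is real and narrow. As written, perceived health risk has no pre-product value, so change from baseline cannot be reported and the ban versus no-ban comparison of this measure cannot be baseline-adjusted. That comparison loses precision but is not biased. The flavor contrast, its moderation by arm and the change from on-product visits to week 12 are unaffected.

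The size is an SE of 0.354 SD where 0.337, 0.306 or 0.252 SD might have been had, i.e. 9%, 25% or 49% of the variance, if the correlation with baseline is 0.3, 0.5 or 0.7. Those correlations are assumptions; the 16 per arm is the plan's own figure. Because the measure is descriptive and in no hypothesis, this is a worthwhile improvement and not a defect that threatens the study's aims.

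**What to change.** Add a perceived health-risk item to the baseline list under Baseline and Evaluation Visits. Word it for e-cigarettes in general, since no product is yet assigned. Have it completed before the assignment is disclosed and before product, instructions and packaging are given. If its wording differs from the later product-specific item, repeat the general item at later visits so that change compares like with like; a covariate does not need this.

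In Data Analysis, state that the baseline value is the reference for change in this measure and a covariate when the measure is compared between the ban and no-ban arms.

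The cost is a few minutes per subject at a visit already held, some rewording, and a minor amendment. Subjects already past baseline would lack the value. If the item is not added, state that for this measure only comparisons between periods, unadjusted comparisons between arms, and comparisons of on-product visits with week 12 are intended.

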Overview: Each subject will attend a screening visit to determine eligibility for the study. If subjects are eligible, they will be scheduled to attend a baseline visit until which they will be asked to continue smoking in their normal manner in order to gather information on their baseline smoking patterns. At the baseline visit, subjects will be randomized to either the 'simulated menthol cigarette ban' or 'no menthol cigarette ban' conditions and additionally will be randomized to the order in which they will receive their assigned e-cigarettes (i.e., menthol flavored e-cigarettes followed by non-menthol tobacco flavored e-cigarette or vice versa). Based on their randomization, subjects will be instructed

as to whether they are to abstain from menthol cigarettes and will be provided a supply of e-cigarettes in the flavor they were randomized to for the first 4 week period. Subjects will be seen at visits scheduled approximately two and four weeks after starting use of their assigned e-cigarettes and will receive a phone call one week after starting use of their e-cigarettes to address any questions that arise. At the week four visit, subjects will receive a supply of the alternate e-cigarette products that they will use for the subsequent four week period. We do not believe that a washout period is needed based on a published cross-over study in which differences were found between menthol and tobacco flavored e-cigarettes after each was used for only a 7 to 10 day period (with no wash-out in between).²² During the second four week period, subjects will again receive a phone call 1 week after starting use of their assigned e-cigarette product and will be seen at visits scheduled two and four week after starting use of their assigned product. In order to ascertain if subjects change their tobacco use behavior once e-cigarettes are no longer provided by the study, subjects will have an additional follow-up visit 12 weeks after the baseline visit (i.e., four weeks after the end of the second assessment period). Subjects who complete the entire study will therefore be seen at a screening visit and 6 additional visits over an approximately 3 month period. The procedures occurring during each of these visits are described below.

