Vuse brand of e-cigarette (manufactured by RJ Reynolds) were selected for this study for several reasons. Studies suggest that as e-cigarette technology evolves, newer products become more effective at delivering nicotine than older products and are perceived as more satisfying.^{16, 28} Vuse is one of the newest and most commonly used products currently on the marketplace. Vuse was introduced nationally in June 2014 and based on reports from May 2015 has achieved the highest market share of any product at 35.7% of the US market.²⁹ Vuse is available in regular and menthol flavor and is therefore appropriate for this investigation.

Screening Visit: All subjects will complete a screening visit prior to enrollment at which written informed consent will be obtained and eligibility will be verified. Medical and psychiatric history will be obtained via subject report. Baseline questionnaires assessing smoking history will be administered. Exhaled carbon monoxide (CO) will be measured to confirm that they are smokers (CO \geq 8 ppm) with a NicCheck performed (with a cut-off of \geq 5) for those who state that they smoke \geq 5 cigarettes per day but for whom CO is less than 8 ppm (e.g., they didn't smoke that morning, they are coming from a smoke free work environment, etc.). Subjects that qualify and are interested in participating will be asked to maintain a paper smoking diary for the duration of the study and will be scheduled for the baseline visit.

Baseline and Evaluation Visits: Subsequent to the screening visit, there will be a baseline visit and four additional evaluation visits scheduled at approximately 2 week intervals (i.e., at 2, 4, 6 and 8 week after the baseline visit). A follow-up visit will occur at week 12 (i.e., 4 weeks after e-cigarettes are no longer provided to subjects).

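### The stated adverse-effect question is phrased in the present tense and tied to visits about 14 days apart, so short-lived events can go unrecorded unless subjects volunteer them

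*Combined protocol and SAP*

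**What the plan says.** The enquiry is one sentence in the approved protocol's Data and Safety Monitoring Plan: "At each visit, subjects will be asked if they are experiencing any adverse effects or difficulties with the study". The next sentence says what the answers are for: "The Principal Investigator will review reports with study staff to determine if changes are needed to any of the study related procedures", or whether a subject should be discontinued. Section 3.0 of the site supplement refers back to this plan for safety monitoring and adds no further enquiry.

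The Implementation Plan puts evaluation visits at about weeks 2, 4, 6 and 8, and a follow-up visit at week 12, four weeks after supply ends. Between visits there is one call in each product period. In the first period, subjects "will receive a phone call one week after starting use of their e-cigarettes to address any questions that arise". In the second, "subjects will again receive a phone call 1 week after starting use of their assigned e-cigarette product".

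On risk, section 11.1 of the site supplement and the Data and Safety Monitoring Plan both warn that "overuse can lead to symptoms of nicotine toxicity such as nausea, vomiting, dizziness, weakness and rapid heartbeat". Both also mention throat irritation and device malfunction. Section 11.1 adds recent reports of seizures and breathing problems.

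**The concern.** Many of the named risks can come and go within two weeks. A question about what the subject has now, asked every two weeks, suits persistent complaints better than brief ones. Section 11.1 was extended to cover seizures and breathing problems, while the monitoring text that should detect such events still rests on the same single sentence.

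At stake is the input to the investigator's review. That review decides on procedural changes and on discontinuation, and it can act only on what is reported. Section 10.1 of the site supplement, which allows withdrawal for certain health changes, likewise depends on staff learning of them. In addition, the Data Analysis section lists the acceptability of both flavors as the first thing the pilot should show for later studies. Adverse effects with dates and flavor attached would inform that.

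**Working it through.** The plan states no figure for adverse-effect capture, so there is none to reproduce. The check has two parts.

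**1. Is there another route of capture?** Each contact or record in the documents was compared with the enquiry.

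- *Daily diary* (Baseline and Evaluation Visits): cigarettes, e-cigarette use and puffs, other tobacco or nicotine products. No symptoms.
- *Visit questionnaires* (same section): craving, withdrawal, motivation, liking, perceived health risk, support for a ban. No adverse-effect items are listed.
- *Calls at weeks 1 and 5* (Overview): the first is for questions the subject may have; no adverse-effect enquiry is stated for either.
- *Contact after a missed visit* (site supplement, section 10.2): wish to continue, reason if not, smoking status.

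None states a symptom enquiry, a look-back window, or onset and end dates.

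**2. How much could a literal reading miss?**

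Inputs from the documents: visits at about days 14, 28, 42, 56 and 84, so gaps of 14 days during supply and 28 days afterwards; calls at about days 7 and 35.

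Assumptions not in the documents: the question is asked strictly about the present, onset is uniform over time, and nothing is volunteered. Episode duration *D* is varied because the documents give none.

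- Share of episodes still present at a visit, gap *L* days: *D/L*.
- Share present at a contact over the 56 supply days if the two calls also asked the present-tense question (6 contacts, *D* up to 7 days): 6*D*/56.

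| Episode length | Visits only, during supply (*D*/14) | Visits plus calls (6*D*/56) | After supply (*D*/28) |
|---|---|---|---|
| 1 hour | 0.3% | 0.45% | 0.15% |
| 1 day | 7% | 11% | 3.6% |
| 3 days | 21% | 32% | 11% |
| 7 days | 50% | 75% | 25% |

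For example, with *D* = 3: 3/14 = 21% and 18/56 = 32%.

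Two things follow. Adding the calls without changing the wording helps only moderately; it is the look-back wording that removes the dependence on a symptom still being present. The calls do cut the time to first enquiry after each product start from 14 to 7 days, which shortens recall.

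**The case against.** The strongest reply is that the sentence summarises a procedure and is not a question script. No script or form is in the file. Staff may well ask about the whole interval, and the mention of difficulties with the study is not naturally confined to the visit day. Section 10.1 presupposes that staff hear of health changes. The supplement also refers to an approved IRB application that is not in the file, and consent pages, which could carry instructions for contact between visits, were removed before review. All of this stands, and it is why the point is about possible loss.

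Four stronger readings are tempting, and the documents do not support them.

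- *That events resolving between visits never reach the investigator.* Subjects can volunteer them at a visit or call, and a seizure is more likely to be mentioned than passing nausea.
- *That this review is the only safety control.* The plan also has health exclusions and a pregnancy test (Subjects), instruction in product use (Baseline and Evaluation Visits), withdrawal for health changes (section 10.1) and no further product in pregnancy (section 11.2).
- *That only 5 of 84 days are covered.* This restates the literal tense as a number and counts the 28 days after supply has ended.
- *That the first enquiry comes after the time when overuse is most likely.* The sentence a reader might rely on, "Providing free product for the entire four week period may result in participants using more of the product than they would otherwise use", explains the points pricing. It says nothing about toxicity or when overuse peaks.

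It is also fair to say that the consequence is limited. Safety is not an aim, and no adverse-effect comparison by flavor is planned that under-counting could bias.

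**Conclusion.** The point holds as a gap in data capture. The only stated enquiry is in the present tense and tied to visits about 14 days apart during supply, and no other described contact or record fills the interval. Short-lived events that the documents themselves name can therefore go unrecorded unless volunteered.

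The size cannot be fixed from the documents. Under the literal assumptions, visits during supply would find roughly 7% of 1-day episodes and 21% of 3-day episodes still present. If staff already ask about the whole interval, or subjects report freely, the loss could be small. No efficacy estimate, test or power figure changes. What is affected is the completeness of the reports on which the investigator's review rests. The change is worth making because it is nearly free, and if interval questioning is already the practice, it only writes that down.

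**What to change.** Reword the question in the Data and Safety Monitoring Plan to cover any adverse effect or device problem since the last contact, including any that have resolved. Record onset date, end date and the e-cigarette flavor in use at the time. Ask the same question at the week 1 and week 5 calls described in the Implementation Plan Overview. Route positive answers from visits and calls into the investigator review that the plan already describes. No new rule on dispensing is needed or proposed.

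The cost is a few minutes of coordinator time per call and a somewhat higher count of minor events, which should be expected when the results are read. No visit, staff member or sample-size change is required.
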